6. STUDY SCHEDULE

Schedule of clinical assessment and procedure:

	Screening	Treatments			
	V 1 Screening & Assessment	V 2 Randomization & 1 st Dose	V 3 2 nd dose	V 4 3 rd dose	V 5 Post Assesments
	-7~1	1 Day	5 week	12 week	24 week
ICF	×				
Eligibility Criteria	×	×			
Baseline Questionnaire	×				
Weight	×		×	×	×
Height	×		×	×	×
Vital Signs	×	×	×	×	×
Vit-D	×			×	
				V4+1 Day	
CD4 count	×			×	
				V4+1 Day	
Viral load	×			×	
				V4+1 Day	
PCR	×			×	
				V4+1 Day	
CBC	×			×	
				V4+1 Day	
Study Medication		×	×	×	
AE Monitoring		×	×	×	×
RDA					×
End of Study					×

6.1 STUDY PROCEDURES AND ASSESSMENTS:

Visit Schedule:

Visit 1 (Screening, Days -3 to 1)

Subjects who were informed about the study and voluntarily gave written consent to participation had the following tests.

- a. Informed consent and screening number assignment
- b. Demographics

- c. Information on exposure to HIV infection
- d. Medical history
- e. Previous HIV lab test if any
- f. RT-PCR
- g. Laboratory tests
- h. Prior medications and therapies
- i. Physical examination (investigator questioning)
- j. Symptoms
- k. Body weight measurement
- l. Assessment of the inclusion/exclusion criteria

Visit 2 (Randomization, Baseline, Day 1):

- a. Medical history
- b. Prior medications and therapies
- c. Physical examination (investigator questioning)
- d. RT-PCR
- e. Laboratory tests
- f. Symptoms
- g. Assessment of the inclusion/exclusion criteria
- h. Randomization
- i. Prescription of test drug or placebo

Visit 3 (Day 4)

- a. Concomitant medications and therapies
- b. Physical examination (investigator questioning)
- c. RT-PCR
- d. Symptoms

e. Treatment adherence.

Visit 4 (Day 7):

a. Concomitant medications and therapies

b. Physical examination (investigator questioning)

c. RT-PCR

d. Laboratory tests

e. Symptoms

Visit 5 (Day 14)

a. Concomitant medications and therapies

b. Physical examination (investigator questioning)

c. RT-PCR

d. Laboratory tests

e. Symptoms

f. Body weight measurement

g. Adverse events

Visit 6 (Day 28):

a. Physical examination (investigator questioning)

b. Laboratory tests

c. AEs

d. Collection of clinical treatment information

Even if a subject was withdrawn, unless the subject withdrew the consent for safety follow-up, the safety follow-up was conducted at the scheduled visits (Visits 3, 4, 5, and 6) to collect the following clinical treatment information.

e. Treatment adherence

Unscheduled Visit:

If a subject arrived at the site for medical treatment on an unscheduled date due to an AE, a change in concomitant drugs, withdrawal status, or measurement data acquired during the research, all relevant facts were documented as thoroughly as possible in the SD. Unplanned visits did not interfere with a planned study schedule. Unscheduled visits may have happened at the subject's solicitation or when the examiner considered it fundamental. There had been no limitations on the tests done during impromptu visits, and the specialist embraced tests that were reasonable and needed for the subject.

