3.1 Sample size calculation

Assuming that 60% of patients in the control arm would attain > 30% of their baseline vitamin-D status at 6 months, we calculated that a total of 94 participants (47 per arm) would need to complete follow-up in order to detect a 25% absolute increase (to 85%) in the proportion of patients attaining > 30% vitamin-D level at 6 months in the intervention arm with 80% power at the 5% significance level. (Lake, Vitamin D in HIV-Infected Patients on HAART, 2014).

This number was inflated to a total of 114 to allow for attrition due to death and loss to follow-up. No interim analysis was performed. (Shriver, 2019)

4. Aims and objectives:

Primary objectives

1. To determine whether proposed oral high dose vitamin D3 is sufficient for achieving the physiological concentration in HIV positive patients on ART. (primary outcome)

Secondary objectives

1. To determine whether this intervention also improves CD4 count, viral load count, liver enzyme in study participants. (Efficacy outcome).
2. To discover whether this interventional regimen is safe and well tolerated by study participants. (Safety outcome).
3. To ascertain socio-demographics factors responsible for decreased level of vitamin D3 in HIV positive patients on ART.

Tertiary objectives:

1. To conclude the effects of total leucocytes count in HIV patients with vitamin D supplementation.
2. To determine the effects of total neutrophil count in HIV patients with vitamin-D supplementation.
3. To determine the effects of total eosinophil count in HIV patients with vitamin-D supplementation.
4. To conclude the effects of total monocyte count in HIV patients with vitamin-D supplementation.
5. To establish the effects of total platelets count in HIV patients with vitamin-D supplementation
6. To find out the effects of total hemoglobin count in HIV patients with vitamin-D supplementation
7. To determine the effects of total lymphocytes count in HIV patients with vitamin-D supplementation
8. To see if the effects of total HCT count in HIV patients with vitamin-D supplementation

5. Outcomes

This section will present the outcomes investigated to answer the study aims and objectives. The analyses are described in section 6 Analyses.

5.1 Primary outcome:

1. To determine whether proposed oral high dose vitamin D3 is sufficient for achieving the physiological concentration in HIV positive patients on ART. (primary outcome)

5.2 Secondary outcomes:

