6.1 Populations

Intention-to-treat (ITT)

All randomised study subjects. This will be seen as the primary population for the analysis.

Per Protocol (PP)

All randomised study subjects completing the whole study period (complete cases). For a specific analysis, study subjects with missing data on any of the variables in the model will be excluded from the analysis. Analyses of this population is seen as a sensitivity analysis to investigate whether conclusions are sensitive to assumptions regarding the pattern of missing data.

6.2 Groups:

Patients with with vitamin-D deficiency are divided into two groups i.e placebo group and vitamin-D group.

Placebo group: out of total 95 participants 47 participants were on placebo arm

Vitamin-D group:

Similar out of total 95 participants 48 participants were on vitamin-D arm

Vitamin-D deficiency:

All randomized study subjects will be divided into two subgroups according to having vitamin-D deficiency at baseline visit.

Division of groups:

All randomised study subjects will be divided into two subgroups according to treatment.

7. Analyses

All outcomes will be presented using descriptive statistics. As the sample size is low so we will check the normality of each variable on screening (Visit 1) and according to the normality check we will determine the mean difference change in Placebo and active treatment arm.

In descriptive analysis we will mention the mean value of each variable with lower and upper bound with 95% confidence interval, 5% trimmed mean, median, Std. Deviation as per the each group ; normally distributed data by the Mean, Variance, Standard deviation (SD), lower and upper values of the variables to see the outliers if any.

In analytical analysis we will apply T-Test for two independent samples to see the difference between two arms. In case any variable doesn't follow the normality assumptions, we will use non-parametric test.

For the safety objective we will use only frequency/number of events to present it.

SPSS 21 will be used for all statistical analysis.

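### Follow-up after withdrawal is described only as safety follow-up, so the week-12 outcome samples needed for the all-randomised primary analysis are not secured

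*Protocol*

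**What the plan says.** Protocol 6.1, in the text around Visit 6, says that for a withdrawn subject "the safety follow-up was conducted at the scheduled visits (Visits 3, 4, 5, and 6) to collect the following clinical treatment information". The exception is "unless the subject withdrew the consent for safety follow-up". The next lettered item is "e. Treatment adherence". No other text in either document says what is measured after withdrawal, and neither document says whether withdrawn means off study medication or out of the study.

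The schedule tables in Protocol 6 and SAP 3 have five visits. Vitamin D, CD4, viral load, PCR and CBC are marked at screening and at V4 (week 12) only. SAP 7.1 to 7.3 analyse change from Visit 1 to Visit 4.

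SAP 6.1 defines the intention-to-treat population as "All randomised study subjects. This will be seen as the primary population for the analysis". It gives no method for missing outcomes in that population. The per-protocol population is the complete cases and serves as the sensitivity analysis for missing data. SAP 3.1 requires 94 completers, and "This number was inflated to a total of 114 to allow for attrition due to death and loss to follow-up".

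**The concern.** An all-randomised analysis needs outcome values from people who stop treatment as well as from those who continue. The plan expects some withdrawn subjects to keep attending, but it gives staff no instruction to draw the outcome sample from them. A site that follows the text could see such a person, record safety information and send them home without the sample.

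Tolerability is a secondary objective, so stopping could plausibly differ by arm. If those who stop have no Visit 4 value, the planned comparison of change can use only those who do. The intention-to-treat and complete-case analyses would then rest on nearly the same people, and agreement between them would say little about missing data. An analysis method can make assumptions about samples that were never drawn, but it cannot recover them.

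**Working it through.** **1. Which visits does the rule cover?** The two visit lists disagree:

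| Visit | Protocol 6.1 narrative | Schedule tables (Protocol 6, SAP 3) |
|---|---|---|
| 3 | Day 4: RT-PCR | Week 5: no outcome bloods |
| 4 | Day 7: RT-PCR, laboratory tests | Week 12: vitamin D, CD4, viral load, PCR, CBC |
| 5 | Day 14: RT-PCR, laboratory tests | Week 24: no outcome bloods |
| 6 | Day 28: laboratory tests | No such visit |

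- Narrative numbering: the rule ends at Day 28 and does not reach week 12. Nor does it reach the other vitamin D times in the Protocol (day 60 in section 5, 24 weeks in section 7).
- Table numbering: the rule reaches V4, but its stated purpose is still safety, and the Visit 6 it names does not exist.

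Neither reading provides for the sample used in SAP 7.1.

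**2. The plan's own sample size.** Inputs from SAP 3.1: 60% and 85%, power 80%, significance level 5% (taken as two-sided). With the unpooled normal approximation:

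n per arm = (1.960 + 0.842)² × (0.60 × 0.40 + 0.85 × 0.15) / 0.25² = 46.15, so 47 per arm and 94 in total. The stated figure is reproduced.

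The total of 114 allows for 114 − 94 = 20 people, and 20/114 = 17.5%. With equal allocation that is 57 randomised and 47 measured per arm, so 10 unmeasured.

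**3. What unmeasured outcomes do to an all-randomised difference (illustration).** Assume m of 57 per arm are unmeasured and the rest respond at 60% and 85%. The lower limit counts every unmeasured active participant as a failure and every unmeasured control as a success; the upper limit does the reverse:

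limits = [0.25 × (57 − m) ± m] / 57

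- m = 0: 25.0 points.
- m = 5: (13 ± 5)/57, that is +14.0 to +31.6 points.
- m = 10: (11.75 ± 10)/57, that is +3.1 to +38.2 points.

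The width is 2m/57, or 3.5 points for each unmeasured participant per arm, whatever the reason. At m = 10 it is 20/57 = 35.1 points, wider than the planned 25-point effect.

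**4. Limits of the illustration.** The value of m is an assumption. The rates are for a responder proportion, whereas SAP 7.1 compares mean change, for which the documents give no standard deviation. The Protocol abstract gives 104 patients; the SAP's 114 is used because the calculation is there.

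**The case against.** The strongest reply is that silence is not prohibition. A reader might infer that vitamin D, CD4 and viral load are not collected after withdrawal, or that the all-randomised population cannot be observed. The documents do not support that. No text says sampling stops. The rule places withdrawn subjects at scheduled visits whose ordinary content includes, at Visit 4 for example, "d. Laboratory tests". For unscheduled visits, "There had been no limitations on the tests done during impromptu visits". This stands, and the point is confined to what the plan fails to provide for. It does not close the gap: the narrative laboratory tests end at Day 28, and tests at unscheduled visits follow the individual subject's need rather than a fixed outcome time in both arms.

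A reader might also take treatment adherence as the complete list of what is collected. That is unsafe. Its letter continues Visit 6's own list, which the withdrawal sentence interrupts, and the list that the sentence announces may be absent or displaced.

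Third, the allowance of 20 is for death and loss to follow-up, not for people who attend off treatment. This also stands: the width in the working cannot be credited to the fix.

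Finally, the lack of a missing-data method for the intention-to-treat population is a separate gap. Filling it would not produce the missing samples.

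**Conclusion.** The concern holds as a gap in provision. The only post-withdrawal follow-up described is for safety, withdrawal is undefined, and on either visit numbering the V4 outcome sample is not provided for in withdrawn subjects who still attend. Outcome data for the SAP's primary population are therefore not secured, and the intention-to-treat analysis would tend towards a completers' analysis.

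Its size cannot be stated from the documents, because they give no number of withdrawn-but-attending participants. The range of about +3 to +38 points shows only what 10 unmeasured of 57 per arm would mean at the planned rates; the share that is avoidable is unknown. The conclusion does not depend on that range. It rests on the absence of any sampling instruction set against the SAP's choice of primary population. The plan should be amended, since the gap is avoidable and cheap to close.

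**What to change.** In Protocol 6.1:

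1. Record stopping study medication and withdrawing consent as separate events, each with its date and reason.
2. State that every randomised participant who has not withdrawn consent has the same outcome bloods as everyone else at the same scheduled time. Under the current table this is V4, week 12, plus any other outcome time scheduled for all. The tables mark no outcome bloods at V5, so the wording should not create a final sample for withdrawn participants alone.
3. State there and in SAP 6.1 that these values are analysed in the randomised arm.
4. Reconcile the Day 4 to 28 visit list with the 5-, 12- and 24-week table, so that Visit 4 has one meaning in the Protocol and the SAP.

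The cost is protocol wording and routine tests for what should be a few extra participants. Those who decline blood sampling remain missing, so the SAP still needs a stated approach for them.

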7. STATISTICAL CONSIDERATION

Statistical analyses will be conducted using SPSS VERSION 23. Qualitative data will be presented in form of frequency and percentage and quantitative data will be presented in form of mean \pm S.D. For the comparison of both treatments (randomly allocated to patients) Wilcoxon test will be applied to compare effectiveness of both treatment plans. P-value ≤ 0.05 will be considered as significant, Baseline characteristics of trial participants will be summarised separately for both randomised group. For each group dichotomous and categorical data of participants will be presented as number and percentages.

The primary outcome, effect of allocation on continuous outcomes that will be assessed both at baseline and at the end of study (e.g. Vitamin-D supplementation at 24 weeks) will be assessed using linear regression, adjusting for the baseline values. The effect of allocation of categorical outcomes variables that will be assessed both at baseline and at the end of study (clinical outcome) will be analysed with generalized linear regression with a log link and binomial distribution to yield a risk ratio adjusted for the baseline

values with 95% CI and p value(**cummings**,2009).. Serum concentration of 25{OH} D will be measured at baseline,05 03 months at baseline, Statistical significance will be inferred where $p < 0.05$.

Allocated to patients) Wilcoxon test will be applied to compare effectiveness of both treatment plans. P-value ≤ 0.05 will be considered as significant.

8. ETHICAL CONSIDERATION

The study will be conducted after approval from the Punjab University Ethical review board. Permission will also be obtained from Punjab AIDS control programme to use health facilities and this study will be registered at CLICAL TRAIL.gov, to use the health facilities and services of paramedics staff for data collection. Written consent of parent and guardian will be taken before starting the study.

8.1 Data Collection

A Performa will be prepared by researcher and finalized after pre-testing. Each patientvisiting Said Mitha Teaching Hospital Lahore will be assessed by the researchers and their demographic information will be noted on the pre-designed Performainitially. Data is collected from all those patients whom would be registered in our 03 months of study after approval of synopsis.

8.2 Human Immunodeficiency Virus

The human immunodeficiency virus (HIV) infects cells of the immune system, destroying or impairing their function. Infection with the virus results in progressive deterioration of the immune system, leading to "immune deficiency."

8.3 Standard Antiretroviral Therapy

Standard antiretroviral therapy (ART) consists of the combination of at least three antiretroviral (ARV) drugs to maximally suppress the HIV virus and stop the progression of HIV disease.

9. ANNEXURE 1: ABBREVIATIONS

AIDS:	Acquired immunodeficiency syndrome
25(OH)vitamin-D:	25 Hydroxy Vitamin-D
RDA:	Recommended daily allowances.
ART:	Anti-retroviral therapy.
HIV:	Human-immune deficiency virus
WHO:	World health organization.
PACP:	Punjab AIDS control programme.
CD4 count:	Cluster of differentiation

(All patients which are not taking vitamin-D Supplementation from last 6 months & having deficiency)

10. Exclusion Criteria

1. pregnant women
2. Patients on active TB medicines
3. Patients do not sign consent form freely

Follow up visits:

11. Treatment obtained:	Yes	No
12. Adverse effects of medicine:	Yes	No
13. Compliance of medicine	Yes	No
14. Outcome of achievement::	Yes	No

Investigator signature:

- 2.** Human immunodeficiency virus (HIV) is a key challenge for global health. Vitamin D deficiency is common in people living with HIV infection. Antiretroviral therapy (ART) may create unique risk factors for vitamin D insufficiency, including alterations of vitamin D metabolism by ART. Vitamin D supplementation in HIV-infected patients have not previously been investigated in Pakistan and it is unknown whether sufficient physiological levels is associated with improved clinical outcome or not. This statistical analysis plan (SAP) will give more detailed descriptions of the endpoints in the study and the corresponding analyses.

- 3. Study design:** We have designed this study with the hypothesis, that the addition of high dose of vitamin D supplementation would be effective in elevating serum 25-hydroxy vitamin D concentration into normal physiological range in patients with HIV infection and this would improve their clinical outcome over the period of 6 months' treatment. The primary outcome of the study will be the sufficient elevating level of serum 25-hydroxyvitamin D at 24weeks. Secondary outcome of the study will be, the increase means CD4 count, decrease in viral load and improvement in liver function test and to reduce the severity of clinical symptoms. This is a double-blind randomized placebo-controlled trial. 114, patients aged (19-50) years with diagnosed HIV disease will be recruited by purposive sampling technique from VCCT treatment centre of Government Said Mitha Teaching Hospital located in the walled city of Lahore, Pakistan. The patients will be divided into two arms. Arm-A patients will receive recommended ARV + Vitamin D supplements and patients in Arm-B will receive recommended ARV and placebo. Participants will be randomly allocated to receive 25 hydroxy vitamin D supplementation (n=) or placebo (n=) with the start of ART

	Screening	Treatments			
	V 1 Screening & Assessment	V 2 Randomization & 1 st Dose	V 3 2 nd dose	V 4 3 rd dose	V 5 Post Assessments
	-7~1	1 Day	5 week	12 week	24 week
ICF	×				
Eligibility Criteria	×	×			
Baseline Questionnaire	×				
Weight	×		×	×	×
Height	×		×	×	×
Vital Signs	×	×	×	×	×
Vit-D	×			×	
CD4 count	×			×	
Viral load	×			×	
PCR	×			×	
CBC	×			×	
Study Medication		×	×	×	
AE Monitoring		×	×	×	×
RDA					×
End of Study					×

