Protocol Title

High-Dose Vitamin D3 in the Treatment of Human Immune Deficiency Virus Patients, A Double-Blind Randomized Control Trial

Protocol Version: 1.0

Date: August 15, 2019

Institute of Social & Cultural Studies
University of the Punjab,
Lahore

Abstract

Human immunodeficiency virus is a key challenge for global health. Vitamin D deficiency is common in people living with HIV infection. Antiretroviral therapy may create unique risk factors for vitamin D insufficiency, including alterations of vitamin D metabolism by ART.

The objective of the study is, to know the effect of high dose Vitamin D, in the treatment of HIV patients with antiretroviral therapy. It will be a randomized controlled trial, in which 104 patients visiting Said Mitha Teaching Hospital Lahore will be included.

The patients will be divided into two groups. Group-A patients will receive ARV + Vitamin D supplements and patients in Group-B will receive only antiretroviral therapy and placebo.

Methods/design: A randomized placebo double blind control trials of patients with age 19-50 years will be the participants of our study at VCCT center of said Mitha Teaching Hospital, located in walled city of Lahore, Pakistan. Participants will be randomly allocated to receive 25 hydroxyvitamin D supplementation (n=) or placebo (n=) with the start of ART.

The primary outcome will be achieved with high dose of serum 25-hydroxyvitamin D level at 24 weeks. Secondary outcome will include decrease in viral load, increase mean CD4 count to reduce prevalence of clinical symptoms (elevated levels of LFTs, decrease HB level & serum calcium level). Purposive sampling will be carried out.

Data will be collected through Performa, which will be entered and statistically analyzed, using SPSS version 24.0, This Performa is designed by the Punjab AIDS Control Programme including socio-demographic information, Pretest

information, posttest information & follow up chart. Chi-square test will be used to estimate the association among qualitative variables.

Discussion: High dose Vitamin D supplementation in HIV-infected patients has not previously been investigated in Pakistan and it is unknown whether increasing levels is associated with improved clinical outcome or not. Therefore, it is significant to conduct a study to know the effect of vitamin D in the treatment of HIV patients with antiretroviral therapy.

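### The planned size is 104 in the protocol and 114 in the SAP, and the 95 in SAP 6.2 is undefined; 104 supports the stated power only if attrition is at most 9.6%

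*SAP*

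**What the plan says.** Three totals stand in the current text.

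- **Protocol, Abstract:** a randomised trial "in which 104 patients visiting Said Mitha Teaching Hospital Lahore will be included". The protocol contains no sample size calculation, so the 104 has no stated basis.
- **SAP 3 and 3.1:** "114, patients aged (19-50) years with diagnosed HIV disease will be recruited". Section 3.1 derives this from 94 completers (47 per arm), sized to "detect a 25% absolute increase (to 85%) in the proportion of patients attaining > 30% vitamin-D level at 6 months", "with 80% power at the 5% significance level". The control rate is set by "Assuming that 60% of patients in the control arm would attain > 30% of their baseline vitamin-D status at 6 months". Then: "This number was inflated to a total of 114 to allow for attrition due to death and loss to follow-up". No attrition rate is given.
- **SAP 6.2:** 47 of 95 participants on placebo, and "Similar out of total 95 participants 48 participants were on vitamin-D arm". The section does not say whether these people were randomised, treated or completed.

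SAP 6.1 defines the ITT population as "All randomised study subjects. This will be seen as the primary population for the analysis" and attaches no number to it. Where the Protocol abstract and SAP 3 would give arm sizes, the available text has a blank. I make no point of the blanks, but they do not settle the matter.

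**The concern.** Two things depend on these totals. The first is power. The SAP adds 20 patients to its 94 completers to cover death and loss to follow-up, and a trial that stops at the protocol's 104 has only 10 of those 20. Anyone recruiting from the protocol could therefore miss the completer target without either document showing it.

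The second is the primary analysis population. ITT is everyone randomised, yet the only group counts in the SAP sum to 95, which matches neither planned total. A reader cannot tell whether 95 is the ITT set or what remains after losses. In the second case, analysing 95 would amount to the complete-case set that the SAP reserves for sensitivity analysis.

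**Working it through.** **Inputs.** Control rate p1 = 0.60, intervention rate p2 = 0.85, power 80%, alpha 5%, 47 completers per arm, inflated total 114 (all SAP 3.1); planned total 104 (Protocol abstract); groups of 47 and 48 (SAP 6.2). The sidedness of the test is not stated, so I assume two-sided. Allocation is 1:1 (Protocol 4.5; SAP 3.1).

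**Step 1: reproduce the SAP's 94.** Unpooled normal approximation, per arm:

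n = [p1(1−p1) + p2(1−p2)] × (1.960 + 0.842)² / (p2−p1)² = (0.2400 + 0.1275) × 7.849 / 0.0625 = 46.15, rounded up to 47, so 94 in total. This matches. Other formulas give slightly more: arcsine 47.64, so 48 per arm; pooled variance 49 per arm.

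**Step 2: attrition implied by each total.**

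- SAP: 1 − 94/114 = 17.5%.
- Protocol: 1 − 94/104 = 9.6%.

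**Step 3: 104 recruited with the SAP's implied attrition.** 104 × 94/114 = 85.8 completers, about 43 per arm.

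**Step 4: power for 60% against 85%.** Unpooled: power = Φ(0.25 / √(0.3675/n) − 1.960).

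- n = 47: 0.25/0.0884 − 1.960 = 0.867, power 80.7%.
- n = 43: 0.25/0.0924 − 1.960 = 0.744, power 77.2%.

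Across methods:

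| Completers per arm | Unpooled | Pooled | Arcsine | Chi-square, exact enumeration |
|---|---|---|---|---|
| 52 (104, no loss) | 84.5% | 82.4% | 83.3% | 83.7% |
| 47 (104 with 9.6% loss, or 114 with 17.5%) | 80.7% | 78.4% | 79.5% | 79.3% |
| 43 (104 with 17.5% loss) | 77.2% | 74.6% | 75.9% | 76.1% |

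Continuity-corrected and Fisher tests give lower power at every size (66.4% and 68.3% at 43 per arm; 72.0% and 72.4% at 47). They do not reproduce the SAP's 94, so I do not use them for the comparison.

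**Step 5: what the 95 could be.**

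- *Completers:* the target of 94 is met. Attrition would be 1 − 95/114 = 16.7%, or 1 − 95/104 = 8.7%. Power at 47.5 per arm is 81.1% unpooled, 78.8% pooled. The ITT denominator is then a larger number that the SAP does not give.
- *Randomised:* 95 is the ITT denominator, and the trial is 9 short of 104 and 19 short of 114. With 17.5% then lost, 95 × 94/114 = 78.3 remain, and pooled power is about 70.5%.

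Nothing in the documents selects between the two.

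**The case against.** The strongest case on the other side is that the power shortfall is conditional and small. The SAP never states 17.5%; it is back-calculated. At 9.6% loss or less, 104 still yields 94 completers. If the 95 are completers, the target was met from either total. By the formula behind the SAP's number the drop is 3.5 points (80.7% to 77.2%), and by the pooled, arcsine and exact chi-square calculations 47 per arm is already slightly below 80%. All of this stands, and it limits the size of the point. It does not remove the contradiction between the planned totals.

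The power figures also belong to a responder comparison, while SAP 7.1 compares mean change from Visit 1 to Visit 4. No standard deviation or mean difference is given, so power for that analysis cannot be computed at any of the three totals. This stands too.

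It might be argued that 114 contains no attrition allowance, because the continuity-corrected formula happens to give 57 per arm, or 114. But SAP 3.1 attributes the increase to attrition, so I take it at its word.

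A reader might go further in two directions that the documents do not support:

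- *That the ITT denominator is wrong.* SAP 6.2 never ties the 95 to ITT, per-protocol or completers. If 95 were randomised, 95 is correct.
- *That the past-tense arm counts show the analysis was chosen after the fact, so the protocol's regression should be restored.* Specific arm counts do suggest late writing, but they reveal no outcome data and do not date the choice of test. The protocol also uses the past tense in places. Nor does it offer one clean method to restore: section 7 names a Wilcoxon test as well as baseline-adjusted regression, and section 4.4 names logistic regression. The protocol's schedule table measures vitamin D only at screening and Visit 4, so a Visit 4 endpoint agrees with that table.

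**Conclusion.** The point holds as an inconsistency in a number the trial relies on. The planned size is 104 in one document and 114 in the other, and 95 appears as a third, unlabelled total. The SAP's own arithmetic is sound: 94 reproduces, and 114 is consistent with inflating it for losses.

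The consequence for power is conditional. With 104, the stated 80% needs attrition of at most 9.6%. At the inferred 17.5% it is about 77% by the SAP's apparent formula, and 75 to 77% across uncorrected methods. This assumes a two-sided test, equal arms and the 60% against 85% responder comparison. It says nothing about power for the mean-change analysis.

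On the analysis population, the supportable conclusion is that the ITT denominator cannot be determined from the documents, not that it is in error.

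**What to change.** - **Planned size.** State one planned randomised number in both documents, with the attrition rate behind it. Either correct the protocol to the SAP's 114, or keep 104 and state that 80% power requires attrition of at most 9.6% and is about 75 to 77% at 17.5%.
- **Scope of the power statement.** In SAP 3.1, say that the power refers to the responder proportion and not to the mean-change comparison in SAP 7.1.
- **Groups.** In SAP 6.2, replace the 95 with the numbers randomised per arm as the ITT groups. Label the 95 as randomised or completers only after the sponsor confirms which it is.

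The cost is wording in both documents and one query to the sponsor. Choosing 114 means 10 more patients than the protocol's figure, but none beyond what the SAP already plans. Keeping 104 adds no patients but makes the power statement less favourable. This point calls for no change to the primary test.
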